8.3. Adverse Event Recording

Any adverse events experienced by the patients in the course of the study will be recorded.

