8.4. Study Visits

8.4.1. Baseline Visit (Month 0)

The patients should be explained the programme in detail before entering the study. Additionally, the following will be obtained and recorded:

- Patients will be confirmed to satisfy all inclusion and exclusion criteria
- Patients will sign the informed consent
- Demographic variables: initials, date of birth, race
- Current clinical history: including the prostate cancer current stage and the treatments received up to the moment of entering the study
- Record of concomitant medications
- Record of concomitant diseases
- Physical examination: including systolic and diastolic blood pressure determination (all the investigators shall use the same model of sphygmomanometer), measurement of the abdominal perimeter (all the investigators shall use the same tape measure), and weight
- Analytical determinations: Glycaemia, HbA1c, Haemoglobin, Lipid profile: total cholesterol, HDL-cholesterol, LDL-cholesterol and triglycerides), Thyroid hormones (TSH), PSA, Total testosterone and C-Reactive protein
- Assessment of Metabolic Syndrome
- Record of the treatment with quarterly LHRH analogues
- Record of adverse events considered to be associated with the LHRH analogues, including local tolerability of the injection

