8.4.2. Follow-up Visits (Month 6 and Month 12)

The following information should be collected and recorded in the CRFs at each visit:

- Physical examination: including measurement of systolic and diastolic blood pressure, measurement of the abdominal perimeter, and weight
- Analytical determinations: Glycaemia, HbA1c, Lipid profile including: total cholesterol, HDL-cholesterol, LDL-cholesterol and triglycerides), Thyroid hormone (TSH), PSA, Total testosterone and C-Reactive protein
- Record of concomitant medications
- Assessment of Metabolic Syndrome
- Record of treatment with quarterly LHRH analogues
- Record of adverse events considered to be associated with the LHRH analogues, including local tolerability of the injection

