9.4.5. Evaluation of Safety

All the safety data will be included in the subjects' data lists. Tabulated analyses and summaries will be based on the general population.

As this is a non-interventional study, only treatment-related Adverse Events (AEs) will be recorded. The AEs will be classified according to the Medical Dictionary for Regulatory Activities (MedDRA), using the term and the organic system class preferred by MedDRA. The AE lists shall be submitted by subject, organic system class and preferred term.

The incidence of all treatment-related emergent AEs (TRAEs) and all SAEs reported will be tabulated. Additionally, tabulated summaries according to maximum severity, relationship with the drug and also AEs/TRAEs associated with early withdrawal of the study medication will be submitted.

TRAE is defined as any AE occurring during the active phase of the study, provided that:

- it had not occurred before receiving the first dose of study drug, or
- it had occurred before receiving the first dose of the study drug but its severity increased in the course of the active phase of the study, or
- it had occurred before receiving the first dose of the study drug, its severity was the same but its relationship to the study drug was established in the course of the active phase of the study.

Treatment-related emergent AEs shall be marked with (*) in the lists of AEs.

Concomitant medication will be coded according to the WHO Drug Dictionary, and summarised including the number and percentage of subjects receiving concomitant medication as <drug class and preferred drug name>.

The statistical summary (mean, median, SD and interval, if applicable) will be displayed by treatment group and also overall regarding heart rate determination and laboratory tests at each assessment, and the changes occurred from baseline will be highlighted. As to the analytical data (including Fasting glucose, HbA1c, Haemoglobin, Triglycerides, Total cholesterol, LDL-cholesterol, HDL-cholesterol, Thyroid hormones (TSH), PSA, Total testosterone, C-Reactive protein), the data printouts will point out at the abnormal values, with a list of those that may be significantly abnormal. Time-progress tables of the amount and percentage of subjects with low, normal or high values or with either normal or abnormal exams will be displayed.

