11.2 Procedure for Recording and Notifying Adverse Reactions

Every adverse reaction, independently of its severity and of its suspected relationship with the study drug, should be recorded in the relevant section of the Case Report Form.

The Investigator should let the Sponsor know any severe adverse reaction within a maximum 24 hours following his/her own awareness of same.

The Sponsor must report the suspected severe adverse reactions to the Competent Authorities within a maximum 15 calendar days from learning about the adverse reaction.

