11.2.1 Adverse Reactions Record

Adverse reaction: Any response to a drug that is harmful and unintended, and occurring at normally-administered doses to humans for prophylaxis, diagnosis or treatment of diseases, or for the restoration, correction or modification of physiological functions. The term also includes all harmful clinical consequences of the dependence, the abuse and the wrong use of drugs, including those consequences caused by drug use under conditions that are not those for which the medicine has been approved, and the ones caused by misadministration (RD 1344 / 2007).

Each investigator will be responsible for evaluating any adverse event (be it spontaneously reported by the patient or objectively detected following a medical questioning) occurring in the course of the study.

If, in the Investigator's opinion, there were or there could be a causal relationship with the study drug and consequently the adverse event were labelled as adverse reaction, the Investigator should state so in the specific form within the Case Report Form (CRF), and report:

- ⇒ date of onset,
- ⇒ length,
- ⇒ intensity: to be assessed with the following classification:

- Mild: an adverse reaction, generally transient, that does not interfere with the patient's normal daily activities.
- Moderate: an adverse reaction that limits the patient's ability to carry out normal daily activities, but does not prevent their performance.
- Severe: an adverse reaction whose unbearable discomfort or pain make carrying out normal daily activities impossible for the patient.

- ⇒ action taken by the doctor (e.g.: none, dose reduction, permanent discontinuation)
- ⇒ outcome (e.g.: death, restoration, improvement, sequels, unknown, etc.)
- ⇒ causality assessment: related, unrelated.

The Investigator should ask the patient “Have you experienced any discomfort since you have been administered the medication?” (or something similar) with the aim to facilitate reporting of potential adverse reactions by the patient.

11.2.2 Adverse Reactions Requiring Immediate Reporting:

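### Adverse-event recording rules conflict (all events versus related only), and the treatment-related category in 9.4.5 does not require causality for new or worsened events

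*Protocol*

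**What the plan says.** The protocol states what is to be recorded in several places.

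- **8.3 Adverse Event Recording:** "Any adverse events experienced by the patients in the course of the study will be recorded". There is no causality filter.
- **8.4.1 Baseline Visit:** "Record of adverse events considered to be associated with the LHRH analogues, including local tolerability of the injection". Section 8.4.2, for Months 6 and 12, has the same item: "Record of adverse events considered to be associated with the LHRH analogues".
- **9.4.5 Evaluation of Safety**, giving the non-interventional design as its reason, sets this limit: "only treatment-related Adverse Events (AEs) will be recorded".
- **11.2**, the section on how adverse reactions are recorded and notified, has this rule: "Every adverse reaction, independently of its severity and of its suspected relationship with the study drug, should be recorded".
- **11.2.1 Adverse Reactions Record:** the specific form is completed on this condition: "If, in the Investigator's opinion, there were or there could be a causal relationship with the study drug". The causality field on that form nevertheless allows both related and unrelated.

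Section 9.4.5 then sets the outputs: the incidence of treatment-related emergent AEs (TRAEs) and of reported SAEs, with summaries by maximum severity, by relationship and for early withdrawal. Its definition begins "TRAE is defined as any AE occurring during the active phase of the study" and is met by any one of three alternatives. The same section bases the safety summaries on a *general population*. The section on definitions of analysis populations does not define that term, and 9.2.1 assigns safety analysis to the treated population.

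**The concern.** An investigator who sees an event and judges it unrelated is told by 8.3 to record it and by 9.4.5 not to. The statistical analysis plan cannot repair this, because the rule decides which data exist, and events never written down cannot be recovered at analysis.

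The second difficulty is the label. *Treatment-related* claims causality, but most of the definition attached to it describes a treatment-emergent event. Whether this does harm depends on which recording rule a site follows.

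Safety reporting is what is at stake. The section on ethical aspects expects the study to yield useful information on drug safety in routine practice. If an incidence mixes two kinds of count, or carries a label that its definition does not support, it cannot serve that purpose.

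**Working it through.** The plan states no figure on this point, so there is none to reproduce. The check is a comparison of the text, followed by a short illustration.

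**Step 1: what happens to an event judged unrelated?**

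| Section | Record it? |
|---|---|
| 8.3 | Yes |
| 8.4.1, 8.4.2 | No |
| 9.4.5 | No |
| 11.2 | Yes by its clause on relationship; unclear by its noun, since 11.2.1 defines an adverse reaction as a response to a drug |
| 11.2.1 | No by its trigger; its causality field implies yes |

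Sections 8.3 and 9.4.5 cannot both be followed. Sections 11.2 and 11.2.1 are each mixed, so neither settles the matter.

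**Step 2: does the TRAE definition require causality?**

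- Limb 1, not present before the first dose: timing only.
- Limb 2, present before but more severe afterwards: worsening only.
- Limb 3, present before at the same severity, with its relationship to the drug established during the active phase: causality is mentioned.

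The limbs are alternatives. A new or worsened event therefore qualifies without any judgement of relationship.

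**Step 3: combine the two.**

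- *All events recorded.* Every new or worsened event, including those judged unrelated, meets limb 1 or 2 and is tabulated as treatment-related.
- *Only related events recorded.* Causality is applied at entry, so the label does little harm. The planned summary by relationship then has essentially one category, and an SAE judged unrelated may not exist as an adverse-event record.
- *Sites differ.* The pooled figure is a mixture of the two.

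**Step 4: illustration of the mixture.** Let A be the incidence of any new or worsened event, R the incidence of related events, and s the share of subjects at sites that record everything. Then

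observed incidence = s × A + (1 − s) × R.

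The protocol gives none of these, so the values are assumptions: A from 40% to 80%, R from 20% to 30%, s = 0.5.

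- A = 40%, R = 20%: 0.5 × 40 + 0.5 × 20 = 30%.
- A = 60%, R = 30%: 0.5 × 60 + 0.5 × 30 = 45%.
- A = 80%, R = 30%: 0.5 × 80 + 0.5 × 30 = 55%.

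At s = 0 the result is R, and at s = 1 it is A. In between, it estimates neither. If every site follows one rule there is no mixing, and the figure is sound provided it is labelled for that rule.

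**The case against.** The strongest defence is that the protocol's working procedure is related-only and that 8.3 is a loose sentence. Sections 8.4.1, 8.4.2, 9.4.5 and the trigger in 11.2.1 broadly agree on this, and 9.4.5 gives the reason: the study is non-interventional. Under that reading the TRAE label is accurate, because relatedness is decided at recording and the limbs only select emergent events. All sites also use one purpose-built case report form, which may settle what is collected.

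Much of this stands. Related-only recording is a legitimate choice, and the form is not shown. It still does not explain the summary by relationship, the unrelated option in the causality field, or the plain wording of 8.3.

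Several stronger readings are tempting but unsupported:

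- **That the TRAE definition contains no causality at all.** Limb 3 refers to relationship to the drug. The accurate statement is that limbs 1 and 2 do not require it.
- **That 11.2 is plainly an all-events rule.** It speaks of adverse reactions and is internally confused.
- **That the SAE table needs unrelated events.** Section 9.4.5 speaks of SAEs that are reported, so the table can be produced under either rule.
- **That an unrelated serious event could never leave a trace.** Section 8.5 (Study Termination by a Patient) lists an adverse event as a reason for leaving, without a causality filter, and dropout reasons go in the case report form. That is a trace, though not a full adverse-event record.

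**Conclusion.** The contradiction is real and stands in current text. Sections 8.3, 8.4, 9.4.5, 11.2 and 11.2.1 must be reconciled, and the TRAE label must be matched to its definition. The mislabelling is conditional: it does harm where all events are recorded and little where only related events are.

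A reader might go further and conclude that the reported incidence will be wrong and will differ by site. The documents support only a risk of this. About 60 centres (section on sample size determination) work from conflicting text, but a single form could impose one rule, and between-site differences would then vanish. The size cannot be computed without event rates, and the percentages in the working are illustrative.

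The consequence is confined to safety reporting. Adverse events are in neither the primary nor the secondary objectives, and the metabolic syndrome analysis and the sample size are untouched. The point is worth correcting because the correction is cheap and determines which safety data are collected.

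**What to change.** 1. State one recording rule in 8.3, 8.4.1, 8.4.2, 9.4.5, 11.2 and 11.2.1. Either choice removes the contradiction:
   - record all adverse events and use the related/unrelated field already in 11.2.1; or
   - record related events only, drop the summary by relationship, and restrict the remaining tables and labels to related events.
2. Use *adverse event* and *adverse reaction* consistently, each in its own sense.
3. In 9.4.5, rename the three-limb category *treatment-emergent AE*, and define *treatment-related* as treatment-emergent with causality recorded as related.
4. In 9.4.5, replace *general population* with the treated population named in 9.2.1.
5. Check that the case report form follows the chosen rule, and tell the sites.

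The cost is protocol wording and a note to sites. The all-events option adds some recording at centres that would otherwise have entered related events only; the documents do not allow that load to be estimated. The related-only option adds no recording but gives up any tabulation of unrelated events.

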8.5. Analysis of Subgroups

Overall descriptive statistics of all of the parameters, and also according to the MS status at the time of entering the study, will be provided.

8.6. Interim Analyses and Data Monitoring

No interim analyses are foreseen.

9. ETHICAL ASPECTS

The CRO will be responsible for Data Management under Ipsen's supervision. In this study, information will be obtained by means of a specifically designed CRF. The information collected will be confirmed to be accurate, consistent and verifiable, through the application of standardised practices and procedures.

Risk-Benefit Assessment for the Research Subjects

Since the patients will receive treatment with LHRH analogues with strict adherence to the indications of the safety sheet on prostate cancer, neither additional benefits nor additional risks to those already known are foreseen. It is expected, however, that a study like the current one will be able to provide very valuable information (in addition to the epidemiological one) on the drug safety within the routine clinical practice for this group of patients, and also improved management and monitoring of androgen deprivation.

9.1. Patient Information Sheet

The Investigator should make sure that the patient is duly informed on the protocol through the Patient Information Sheet and through the information supplied by the Investigator him/herself.

Before including a patient in the study, the physician should obtain the patient's informed consent to participate.

9.2. Confidentiality of the Data

With the aim of guaranteeing confidentiality, the patients will be identified on the CRF by their initials and their date of birth only.

According to European Directive 95/46/CE on the protection of persons regarding personal data processing, and Spanish Law 15/1999 on Personal Data Protection, patients' personal data will be confidential and delivery of such data to third parties who are different from those already mentioned is specifically prohibited, with the only exception of the existence of a signed agreement among all the interested parties.

Should the patient request so, medical information will be provided to his/her family doctor or to the health professional responsible for his/her welfare.

All the information generated by this study should remain available for inspection by Ipsen's authorised staff, by the local and national authorities, by the Personal Data Protection Body or by the Ethics Committees.

9.3. Interference with Prescription Practices

Only patients strictly satisfying the indications for LHRH analogues, and who in the Investigator's opinion will obtain a benefit from the treatment, will be included in the study.

11. PRACTICAL CONSIDERATIONS

11.1. Work Plan

Patient's informed consent should be available before undertaking any study-related assessment.

The investigators to participate in ANAMET should meet the requirements below and/or provide Ipsen with the following information:

- Information on the centre:
Name, position, address, telephone and fax numbers of the principal investigators and of the collaborating investigators, the study co-ordinators or any other staff responsible for the study conduct at the centre.
- Having signed an agreement with reference to ANAMET (by the centre or by the Investigator, as applicable) in which the participation of the Investigator in the study is mentioned.
- Having obtained the relevant Ethic Committees and Autonomic Communities approvals.

Patients will be controlled on an outpatient basis throughout the study.

The performance of the study is schematised as follows:

STUDY SCHEME

	Baseline (V0)	Month 3	Month 6 (V2)	Month 9	End Visit Month 12 (V3)
Inclusion/Exclusion Criteria	+				
Informed Consent	+				
Demography	+				
Case history and concomitant diseases	+				
Blood pressure	+		+		+
Abdominal perimeter	+		+		+
BMI, weight, height	+		+		+
Prior and concomitant medication	+		+		+
Laboratory tests*	+		+		+
Treatment	+	+	+	+	+
Adverse Events	+		+		+

* **Laboratory tests:** Glycaemia, HbA1c, Hb, Lipid Profile (Total, HDL and LDL cholesterol, and triglycerides), Thyroid hormone (TSH), C-reactive protein, PSA and Total testosterone.

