4. STUDY RATIONALE: CRITICAL REVIEW OF LITERATURE

4.1 Review of the Disease

4.1.1. Prostate Cancer

Prostate cancer is currently considered one of the most frequent cancers in men (first in incidence and third in mortality) (1). Most of the cases are localised cancers at the time of diagnosis, and so apt to be adequately treated with surgery and/or radiation therapy (brachytherapy, external-beam radiation therapy, etc.).

More than one third of them appear in locally advanced stages, notwithstanding the screening campaigns. These patients, generally with stages T3 (capsule involvement, vesicle involvement), T4 (nearby organ involvement), N+ (nodal involvement) or M+ (distant, basically bone, involvement), will be candidates to treatment with either complete or partial hypothalamic-pituitary axis blockade.

Indications for hormone blockade are the following: a) as the first option in systemic disease; b) as adjuvant following curative pelvic-prostatic radiation therapy for 2-3 consecutive years; c) as neoadjuvant prior to a 6-month radiation therapy treatment.

Two/three-year treatment concomitant to radiation therapy yields 5- and 8-year disease-free survival rates of around 78% in high-risk locally-advanced disease (Gleason histological grade equal to or higher than 8, PSA > 20 ngr, T equal to or higher than 3, N +, M0).

Treatment with LHRH agonists is not devoid of adverse reactions. In some cases there is a transient exacerbation of the clinical symptoms (basically bone pain) when treatment starts. Some cases of worsening of a preexisting haematuria, or urinary obstruction and/or a sensation of weakening or paresthesia of the lower limbs have been described with the LHRH analogues at treatment initiation. These symptoms are generally transient and they disappear on the first or the second week without requiring treatment discontinuation. In any case, the possibility of an initial symptom exacerbation should be born in mind when treating neurologically affected patients or patients suffering from urinary obstruction.

The following adverse reactions have been described during the treatment: hot flushes, pain at the site of injection, erectile dysfunction and transiently elevated arterial blood pressure that resolves spontaneously.

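### Adverse-event enquiry is scheduled only at Months 0, 6 and 12, so non-severe reactions to the Month 0 and Month 6 injections may first be asked about up to six months later

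*Protocol*

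**What the plan says.** The study scheme in Protocol 11.1 has a treatment row marked at Baseline and Months 3, 6, 9 and 12. The row "Adverse Events" is marked at Baseline, Month 6 and Month 12 and is blank at Months 3 and 9.

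The visit descriptions agree. Sections 8.4.1 and 8.4.2 describe visits at Months 0, 6 and 12 only. The safety item at each follow-up visit is "Record of adverse events considered to be associated with the LHRH analogues, including local tolerability of the injection".

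Section 4.1.1 describes the reactions the protocol has in mind. Of the symptoms seen in some patients at the start of treatment it says: "These symptoms are generally transient and they disappear on the first or the second week without requiring treatment discontinuation". Among reactions during treatment it lists "hot flushes, pain at the site of injection, erectile dysfunction".

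Three provisions apply between visits. Section 8.3 (Adverse Event Recording) says: "Any adverse events experienced by the patients in the course of the study will be recorded". Section 11.2.1 has the investigator evaluate each event, "be it spontaneously reported by the patient or objectively detected following a medical questioning". Section 11.2 requires severe reactions to reach the sponsor within 24 hours of the investigator learning of them.

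**The concern.** Several of the reactions described in 4.1.1 are brief, and the enquiry schedule is long by comparison. Baseline is where treatment starts, so the record made there can hold little about the first injection. The next scheduled enquiry is Month 6, with a treatment point at Month 3 in between that carries no adverse-event record.

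The protocol asks for detail that depends on memory. Section 11.2.1 requires date of onset, length and intensity for each reaction, and gives an open question about discomfort after dosing to help the patient report. Section 9.4.5 then tabulates incidence, maximum severity and relationship to the drug. The risk-benefit paragraph under Ethical Aspects names drug-safety information from routine practice as something the study is expected to yield.

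What is at stake is how complete and reliable those descriptive safety tables are for mild and moderate transient reactions.

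**Working it through.** The protocol states no figure for this interval, so there is nothing to reproduce. The check compares two rows of the study scheme and subtracts.

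**Inputs**
- Treatment points: Months 0, 3, 6, 9, 12 (11.1).
- Scheduled adverse-event enquiry: Months 0, 6, 12 (11.1; 8.4.1 and 8.4.2 agree).
- End of early symptoms: week 1 or 2 after treatment start (4.1.1).
- Conversion: Month 6 is about week 26 and Month 3 about week 13 (52 weeks / 12 months).

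**Step 1. Gap = month of next scheduled enquiry minus month of injection.** An enquiry on the day of an injection is taken to look back, not forward; hence up to six months for the injections at Months 0 and 6.

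| Injection | Next enquiry as planned | Gap (months) | Next enquiry if Months 3 and 9 are added | Gap (months) |
|---|---|---|---|---|
| Month 0 | Month 6 | 6 - 0 = 6 | Month 3 | 3 - 0 = 3 |
| Month 3 | Month 6 | 6 - 3 = 3 | Month 6 | 6 - 3 = 3 |
| Month 6 | Month 12 | 12 - 6 = 6 | Month 9 | 9 - 6 = 3 |
| Month 9 | Month 12 | 12 - 9 = 3 | Month 12 | 12 - 9 = 3 |

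The longest gap falls from 6 to 3 months. The gain is all at the Month 0 and Month 6 injections; the gap after the Month 3 and Month 9 injections stays at three months.

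**Step 2. Recall of early symptoms = week of first enquiry minus week the symptom ends.**
- As planned: 26 - 2 = 24 to 26 - 1 = 25 weeks.
- With a Month 3 enquiry: 13 - 2 = 11 to 13 - 1 = 12 weeks.

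**Step 3. Does anything else schedule an enquiry in between?** Sections 8.3, 11.2 and 11.2.1 set duties to record, evaluate or notify once something has been reported or detected. None of them places an enquiry at Month 3 or Month 9. They cover volunteered and severe reactions, and leave the gap for non-severe reactions that come to light only when the patient is asked.

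Treatment is also marked at Month 12, with no later enquiry. A reaction to any injection given then would have no scheduled capture, and the change proposed here would not alter that.

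**The case against.** The best case for the plan is that this is a coherent choice. The study is observational and follows usual practice. The scheme and 8.4 agree with each other, Months 3 and 9 carry no visit number and no assessment, and safety is not among the objectives in section 5. Events are summarised descriptively, and no test depends on them. All of this stands: the point is a design weakness in a descriptive output, not a contradiction.

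Four stronger readings are tempting, and the documents do not support them.

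- A reader might infer that nothing is collected between visits. Sections 8.3, 11.2 and 11.2.1 say otherwise: a reaction volunteered at a Month 3 injection should be recorded.
- A reader might measure the problem by counting the two treatment points without a tick. Those injections have the three-month gaps; the six-month gaps follow Months 0 and 6, so that count does not measure the recall problem.
- A reader might conclude that reactions will be under-reported and their details unreliable. That is a reasonable worry, but no figure in the protocol supports a size or makes it certain. Section 4.1.1 also describes the early symptoms as occurring in some cases only.
- A reader might assume that the investigator sees every patient at Months 3 and 9. A treatment tick does not say who gives the injection or where.

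It is also fair to say that the remedy is partial: early symptoms would still be asked about some 11-12 weeks after they end.

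**Conclusion.** The point holds for solicited, non-severe reactions. Scheduled enquiry comes up to six months after the Month 0 and Month 6 injections, about 24-25 weeks after early symptoms that last one to two weeks, and three months after the Month 3 and Month 9 injections. This may lower ascertainment and the reliability of onset, length and intensity in the safety tables of 9.4.5.

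The intervals are exact given the scheme. The effect on reporting is an inference whose size cannot be derived from the protocol. The conclusion assumes that injections and visits fall at their nominal months and that the Baseline and Month 6 enquiries do not cover the injection given on the same day. The primary endpoint, metabolic syndrome prevalence, is not affected. The change is inexpensive and worth making.

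**What to change.** In the study scheme (11.1), mark adverse events at Months 3 and 9, and add the matching entry to 8.4 (Study Visits). At those two treatment points, when the patient attends the participating service, record the answer to the existing question in 11.2.1 and local tolerability, both covering the period since the previous injection. Ask for no extra contact where the injection is given elsewhere. No test, visit or change of treatment is involved.

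The cost is a short additional case report form entry at two points. Coverage will be incomplete for patients injected away from the service, so the report should state how many patients had a Month 3 and a Month 9 record.
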